3.3 Inclusion of Women, Minorities and Other Underrepresented Populations

CLL is approximately twice as common in men as women, but women have generally been well represented on our CLL protocols at DFCI and the CRC. The eligibility criteria will not have a

CONFIDENTIAL

This document is confidential. Do not disclose or use except as authorized.

negative impact on enrollment of women, particularly since most women with CLL are postmenopausal. We will make every effort to enroll minorities on this study although few are seen in our clinic.

4. REGISTRATION PROCEDURES

4.1 General Guidelines for DF/HCC and DF/PCC Institutions

Institutions will register eligible participants with the DF/HCC Quality Assurance Office for Clinical Trials (QACT) central registration system. Registration must occur prior to the initiation of therapy. Any participant not registered to the protocol before treatment begins will be considered ineligible and registration will be denied. All subjects should also be registered to the CLL Research Consortium tissue bank but this enrollment will be through a separate protocol at each institution.

An investigator will confirm eligibility criteria and a member of the study team will complete the QACT protocol-specific eligibility checklist. Following registration, participants may begin protocol treatment. Issues that would cause treatment delays should be discussed with the Overall Principal Investigator (PI). If a participant does not receive any protocol therapy following registration, the participant's registration on the study may be canceled. Notify the QACT Registrar of registration cancellations as soon as possible.

4.2 Registration Process for DF/HCC and DF/PCC Institutions

The QACT registration staff is accessible on Monday through Friday, from 8:00 AM to 5:00 PM Eastern Standard Time. In emergency situations when a participant must begin treatment during off-hours or holidays, call the QACT registration line at [contact] and follow the instructions for registering participants after hours.

The registration procedures are as follows:

1. Obtain written informed consent from the participant prior to the performance of any study related procedures or assessments.
2. Complete the QACT protocol-specific eligibility checklist using the eligibility assessment documented in the participant's medical record and/or research chart. **To be eligible for registration to the protocol, the participant must meet all inclusion and exclusion criterion as described in the protocol and reflected on the eligibility checklist.**

Reminder: Confirm eligibility for ancillary studies at the same time as eligibility for the treatment study. Registration to both treatment and ancillary studies will not be completed if eligibility requirements are not met for all studies.

CONFIDENTIAL

This document is confidential. Do not disclose or use except as authorized.

3. Fax the eligibility checklist(s) and all pages of the consent form(s) to the QACT at [contact].
4. The QACT Registrar will (a) review the eligibility checklist, and (b) register the participant on the protocol.
5. An email confirmation of the registration will be sent to the Overall PI, study coordinator(s) from the Lead Site, treating investigator and registering person immediately following the registration.

4.3 General Guidelines for Other Participating Institutions

Eligible participants will be entered on study centrally at the DFCI by the Study Coordinator. All sites should call the Study Coordinator to verify treatment availability. The required Eligibility Checklist can be found in Appendix B.

Following registration, participants should begin protocol treatment within 5 days. Issues that would cause treatment delays should be discussed with the Overall PI. If a participant does not receive protocol therapy following registration, the participant's registration on the study may be canceled. The DFCI study team should be notified of cancellations as soon as possible.

4.4 Registration Process for Other Participating Institutions

To register a participant, the following documents should be completed by the research nurse or data manager and faxed or emailed to the DFCI central email ([contact]), Project Manager and Study Coordinator:

- Copy of all screening test results, CT scan, BM report
- Signed study consent form
- HIPAA authorization form
- Signed eligibility checklist

The research nurse or data manager at the participating site will then call the Project Manager or email the DFCI central email ([contact]) to verify eligibility.

To complete the registration process, the Project Manager will:

- Register the participant on the study with QACT
- Fax or e-mail the participant study number, and if applicable the dose treatment level, to the participating site
- Call the research nurse or data manager at the participating site and verbally confirm registration

Note: Registration with the QACT can only be conducted during the business hours of 8am – 5pm EST Monday through Friday. Same day treatment registrations will only be accepted with prior notice and discussion with DFCI.

CONFIDENTIAL

This document is confidential. Do not disclose or use except as authorized.

5. TREATMENT PLAN

Treatment will be administered on an outpatient basis. Expected toxicities and potential risks as well as dose modifications for ofatumumab are described in Section 6 (Expected Toxicities and Dosing Delays/Dose Modification). No investigational or commercial agents or therapies other than those described below may be administered with the intent to treat the participant's malignancy.

Idelalisib lead-in followed by ofatumumab 8 wks later

All therapy with idelalisib has been discontinued. Patients on drug stopped as of 3/11/16. Those currently receiving ofatumumab may complete the planned course and evaluations as below. Those who have not yet reached day 57 may initiate ofatumumab at present. On day 57, ofatumumab will begin with the 300 mg dose. Ofatumumab will then be administered at 1000 mg weekly to complete 8 weeks (days 64, 71, 78, 85, 92, 99, 106) throughout Cycles 3 and 4. Cycle 4 will last 49 days (7 weeks) to accommodate the Ofatumumab dosing schedule. This will be followed by monthly ofatumumab on weeks 20, 24, 28, 32 to complete 4 additional cycles (5-8). The overall induction treatment period will then be up to 8 months, including whatever idelalisib was received prior to March 11, 2016. Restaging with CT scans will happen after Cycle 2, on cycle 4 day 22, and a final restage will occur 2 months after the completion of ofatumumab. There will be a tumor response assessment done via physical exam after Cycle 8.

Table 1: Treatment Description

Agent	Pre-medications; Precautions	Dose	Route	Schedule	Cycle Length
Idelalisib	None	150 mg BID	Oral	Discontinued	28 days (4 weeks) (Except cycle 4-49 days, 7 weeks)
Ofatumumab	Pre-medication before each ofatumumab infusion must be given within 30 minutes to 2 hours prior to the treatment: Acetaminophen 1000 mg po Benadryl 50 mg IV or po Methylprednisolone 50 mg IV*	300 mg at 0.3 mg/ml in NS; followed one week later by 1000 mg at 1 mg/ml in NS	IV after administration of Idelalisib and premeds	Weekly x 8 doses, then monthly x 4 doses	
* If the 2 nd infusion has been completed without the subject experiencing any grade = 3 AEs, pre-medication with glucocorticoid may be reduced or omitted before the 3 rd to N th infusion at the discretion of the investigator.					

CONFIDENTIAL

This document is confidential. Do not disclose or use except as authorized.

5.1 Pre-treatment Criteria

5.1.1 Cycle 1, Day 1

Subjects must continue to meet the laboratory eligibility criteria for creatinine and LFTs. Subjects must have initiated infectious prophylaxis; they also must be monitored and/or receive prophylaxis against tumor lysis syndrome as needed at the discretion of the treating physician. See section 5.3.2 and 5.3.6 for additional details.

5.1.2 Subsequent Cycles

Liver function tests, creatinine, and complete blood count with differential must be reviewed prior to administration of ofatumumab therapy and managed as below under toxicity management. Premedication for ofatumumab during cycles 3-8 must be given as per Table 1 above.

5.2 Agent Administration

5.2.1 Idelalisib will not be given

5.2.2 Ofatumumab

The dosing of ofatumumab in CLL should consist of an infusion of 300 mg on Day 1, an infusion of 1000 mg weekly for 7 additional doses, and then infusions of 1000 mg monthly for up to 4 doses. The monthly ofatumumab doses should be given on Day 1 of the cycles.

First Infusion of 300 mg Ofatumumab (CLL)

The first dose administered of ofatumumab in CLL should be 300 mg to minimize infusion reactions. The initial rate of the first infusion of 300 mg ofatumumab (0.3 mg/mL) should be 12 mL/h. If no infusion reactions occur the infusion rate should be increased every 30 minutes, to a maximum of 400 mL/h, according to Table 2. If this schedule is followed, the infusion duration will be approximately 4.6 hours. If the ofatumumab dose cannot be completed on day 1 in clinic, the remaining dose may be completed the following day with the same premedications.

Table 2: Infusion rate at 1st ofatumumab infusion (300 mg)

Time	mL/hour
0 – 30 minutes	12
31 – 60 minutes	25
61 – 90 minutes	50
91 – 120 minutes	100
121 - 150 minutes	200
151 - 180 minutes	300
181+ minutes	400

CONFIDENTIAL

This document is confidential. Do not disclose or use except as authorized.

If an infusion reaction develops, the infusion should be temporarily slowed or interrupted. Upon restart, the infusion rate should be half of the infusion rate at the time the infusion was paused. If, however, the infusion rate was 12 mL/hour before the pause, the infusion should be restarted at 12 mL/hour. Thereafter, the infusion rate may be increased according to the judgment of the investigator, in the manner described in this section. If the infusion is not completed on day 1, the remaining infusion may be completed on day 2 at the starting infusion rate used on day 1.

First Infusion of 1000 mg Ofatumumab

The initial rate of the first infusion of 1000 mg ofatumumab (1 mg/mL) should be 12 mL/h. If no infusion reactions occur the infusion rate should be increased every 30 minutes, to a maximum of 400 mL/h, according to Table 3. If this schedule is followed, the infusion duration will be approximately 4.6 hours. If the ofatumumab dose cannot be completed on day 1 in clinic, the remaining dose may be completed the following day with the same premedications.

Table 3: Infusion rate at 1st ofatumumab infusion (1000 mg)

Time	mL/hour
0 – 30 minutes	12
31 – 60 minutes	25
61 – 90 minutes	50
91 – 120 minutes	100
121 - 150 minutes	200
151 - 180 minutes	300
181+ minutes	400

If an infusion reaction develops, the infusion should be temporarily slowed or interrupted. Upon restart, the infusion rate should be half of the infusion rate at the time the infusion was paused. If, however, the infusion rate was 12 mL/hour before the pause, the infusion should be restarted at 12 mL/hour. Thereafter, the infusion rate may be increased according to the judgment of the investigator, in the manner described in this section. If the infusion is not completed on day 1, the remaining infusion may be completed on day 2 at the starting infusion rate used on day 1.

Subsequent Infusions of 1000 mg Ofatumumab

If the previous infusion has been completed without grade ≥ 3 infusion-associated AEs, the subsequent infusion of the 1000 mg ofatumumab (1 mg/mL) can start at a rate of 25 mL/hour and should be doubled every 30 minutes up to a maximum of 400 mL/h, according to Table 4. Duration of the infusion will be approximately 4 hours if this schedule is followed. If the previous infusion has been completed with grade ≥ 3 infusion-associated AEs, the subsequent infusion should start at a rate of 12 mL/hour according to Table 3 for CLL.

Table 4: Infusion rate at subsequent ofatumumab infusion

Time	mL/hour
0 – 30 minutes	25
31 – 60 minutes	50

CONFIDENTIAL

This document is confidential. Do not disclose or use except as authorized.

61 – 90 minutes	100
91 – 120 minutes	200
121+ minutes	400

During infusion the participant should be monitored closely and appropriate measurements should be performed whenever judged necessary. If the ofatumumab dose cannot be completed on day 1 in clinic, the remaining dose may be completed the following day with the same premedications. If the infusion is not completed on day 1, the remaining infusion may be completed on day 2 at the starting infusion rate used on day 1.

5.3 General Concomitant Medication and Supportive Care Guidelines

To the extent possible, administration of any prescription or over-the-counter drug products other than study medication should be minimized during the study period. Participants should be discouraged from use of recreational drugs, herbal remedies, self-prescribed drugs, tobacco products, Tylenol or excessive alcohol at any time during the clinical study.

If considered necessary for the participant's well-being, drugs for concomitant medical conditions or for symptom management may be given at the discretion of the investigator. The decision to authorize the use of any drug other than study drug should take into account participant safety, the medical need, the potential for drug interactions, the possibility for masking symptoms of a more significant underlying event, and whether use of the drug will compromise the outcome or integrity of the study

Participants should be instructed about the importance of the need to inform the clinic staff of the use of any drugs or remedies (whether prescribed, over-the-counter, or illicit) before and during the course of the study. Any concomitant drugs taken by a participant during the course of the study and the reason for use should be recorded on the CRFs.

Information regarding use or restrictions on specific concomitant medications, dietary measures, or other interventions is provided below.

5.3.1 Antiemetics

Nausea and/or vomiting have not been commonly observed with ofatumumab in prior studies. However, participants who experience nausea or vomiting while on study therapy may receive antiemetics based on the judgment of the treating physician and local institutional practices. At the occurrence of persistent nausea or vomiting of severity grade ≥ 1 , it is suggested that the participant receive an oral or transdermal serotonin antagonist (eg, dolasetron, granisetron, ondansetron, tropisetron, palonosetron). The neurokinin receptor antagonist, aprepitant, may be considered but is a mild inhibitor of CYP3A4 and so may modestly increase idelalisib plasma exposures. Other classes of antiemetic medications that may be employed include dopamine antagonists or benzodiazepines. If possible, systemic corticosteroids should be avoided other than as premedication for ofatumumab.

5.3.2 Tumor Lysis Prophylaxis

CONFIDENTIAL

This document is confidential. Do not disclose or use except as authorized.

Subjects initiating each study drug should be given allopurinol 300 mg daily for approximately 10 days unless contra-indicated, and tumor lysis laboratory testing should be done at the discretion of the treating investigator. Allopurinol therapy should continue through ofatumumab therapy. If allopurinol is contra-indicated another uric acid reducing agent may be substituted or alternative plans may be discussed with the overall principal investigator. Intravenous fluid prophylaxis may also be given at the discretion of the treating investigator and is recommended at the time of initiating therapy with both idelalisib and again with ofatumumab initiation at cycle 3 day 1.

5.3.3 Granulocyte Colony-Stimulating Factors and Erythropoietin

Granulocyte-macrophage colony-stimulating factor (GM-CSF) should not be administered given the potential for GM-CSF-related inflammatory symptoms. Granulocyte colony-stimulating factor (G-CSF) agents including pegfilgrastim if desired and erythropoietic agents (eg, erythropoietin or darbepoetin) may be administered in response to Grade ≥ 3 neutropenia or anemia, respectively. Such use should be particularly considered if providing hematopoietic support might help to maintain idelalisib-ofatumumab therapy. Reference should be made to the American Society of Clinical Oncology guidelines [49, 50].

5.3.4 Contraception

In the context of this protocol, a female subject is considered to be of child-bearing potential unless she has had a hysterectomy, a bilateral tubal ligation, or a bilateral oophorectomy; has medically documented ovarian failure (with serum estradiol and FSH levels within the institutional postmenopausal range and a negative serum or urine β HCG); or is menopausal (age ≥ 55 years with amenorrhea for ≥ 6 months).

Sexually active females of child-bearing potential must accept continuous heterosexual abstinence as a lifestyle choice or agree to use a protocol-recommended method of contraception during heterosexual intercourse throughout the study treatment period and for 30 days from the last dose of study drug or 12 months from the last dose of ofatumumab (whichever is later). The investigator should counsel subjects on the most effective methods for avoiding pregnancy during the trial. Protocol-recommended contraceptive methods are described in table below.

Protocol-Recommended Contraceptive Methods

Individual Methods	Combination Methods	
	Hormonal Methods (One method to be used with a barrier method)	Barrier Methods (Both of these methods to be used OR one of these methods to be used with a hormonal method)
IUD	Estrogen and progesterone	Diaphragm with spermicide
Copper T 380A IUD	Oral contraceptives	Male condom (with spermicide)
LNg 20 IUD	Transdermal patch	
Tubal sterilization	Vaginal ring	
Hysterectomy	Progesterone	
	Injection	
	Implant	

Abbreviation: IUD=intrauterine device

CONFIDENTIAL

This document is confidential. Do not disclose or use except as authorized.

In the context of this protocol, a male subject is considered able to father a child unless he has had a bilateral vasectomy with documented aspermia or a bilateral orchiectomy, or is receiving ongoing testicular suppression with a depot luteinizing hormone-releasing hormone (LH-RH) agonist (eg, goserelin acetate [Zoladex®]), leuprolide acetate [Lupron®], or triptorelin pamoate [Trelstar®]).

Sexually active male subjects who can father a child must accept continuous heterosexual abstinence as a lifestyle choice; limit intercourse to female partners who are surgically sterile, post-menopausal, or using effective contraception (as noted in table above); or agree to use a protocol-recommended method of contraception during heterosexual intercourse throughout the study treatment period and for 90 days following discontinuation of idelalisib (as noted in table above).

The Gilead Sciences medical monitor should be consulted regarding any questions relating to child-bearing status or contraception.

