- 3.1.1 The effects of idelalisib and ofatumumab on the developing human fetus are unknown. For this reason, women of child-bearing potential and men must agree to use adequate contraception (hormonal or barrier method of birth control; abstinence) prior to study entry and for the duration of study participation. Females of childbearing potential must agree to use a

CONFIDENTIAL

This document is confidential. Do not disclose or use except as authorized.

protocol-recommended method of contraception during heterosexual intercourse from the screening visit throughout the study and for 30 days from the last dose of idelalisib. Should a woman become pregnant or suspect she is pregnant while participating in this study, she should inform her treating physician immediately.

3.1.2 Ability to understand and the willingness to sign a written informed consent document.

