- 3.2.11 Clinically significant cardiac disease including unstable angina, acute myocardial infarction within six months prior to randomization, congestive heart failure (NYHA III-IV), and arrhythmia unless controlled by therapy, with the exception of extra systoles or minor conduction abnormalities.
- 3.2.12 Significant concurrent, uncontrolled medical condition including, but not limited to, renal, hepatic, gastrointestinal, endocrine, pulmonary, neurological, cerebral or psychiatric disease which in the opinion of the investigator may represent a risk for the participant.
- 3.2.13 Positive serology for Hepatitis B (HB) defined as a positive test for HBsAg. In addition, if negative for HBsAg but HBcAb positive (regardless of HBsAb status), a HB DNA test will be performed and if positive the subject will be excluded.
- *If HBV DNA is negative, subject may be included but must undergo HBV DNA PCR testing at least every 2 months from the start of treatment until 12 months post treatment. Prophylactic antiviral therapy may be initiated at the discretion of the investigator.
- 3.2.14 Positive serology for hepatitis C (HC) defined as a positive test for HepC Ab, in which case reflexively perform an HC RIBA immunoblot assay or hepatitis C viral load to confirm the result. If the confirmatory test is negative the subject will be eligible.
- 3.2.15 Pregnant or lactating women. Women of childbearing potential must have a negative pregnancy test at screening. Pregnant women are excluded from this study because idelalisib and ofatumumab are anti-neoplastic agents with the potential for teratogenic or abortifacient effects. Because there is an unknown but potential risk of adverse events in nursing infants secondary to treatment of the mother, breastfeeding should be discontinued if the mother is treated on this study with idelalisib and ofatumumab.
- 3.2.16 Women of childbearing potential, including women whose last menstrual period was less than one year prior to screening, unable or unwilling to use adequate contraception from study start to 30 days after the last dose of protocol therapy. Adequate contraception is defined as hormonal birth control, intrauterine device, double barrier method or total abstinence.
- 3.2.17 Male subjects unable or unwilling to use adequate contraception methods from study start to 30 days after the last dose of protocol therapy.

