Banking at Clinical Research Consortium for Sites not participating in a CRC study ¹⁸	X		C 3 D1						X	
PK samples, ofatumumab ⁵			C3 D1, 8, 15; C4 D 22	CYCLE 5 D 1 & CYCLE 8 D 1		FINAL ONLY		6 MOS		
PK samples, idelalisib ⁵		DAY 1 EACH CYCLE	CYCLE 3 DAY 1, CYCLE 4 DAY 22	CYCLE 8 DAY 1		FINAL ONLY		6 MOS		
OSU Studies ⁶	X	CYCLE 1 DAY 1, 15; CYCLE 2 DAY 1	CYCLE 3 DAY 1			TWO MONTH ONLY				
Mayo Studies ⁷	X		CYCLE 3 DAY 1			FINAL ONLY			EVERY 6 MONTHS FOR FIRST YEAR; & AT PD	
Physical Exam	X	WEEKLY	CYCLE 3 DAY 1, 8, 15, CYCLE 4 DAY 1, 15	MONTHLY	X	X	X	X	X	
ECOG	X	WEEKLY	WITH PE	WITH PE	X	X	X	X		
Height	X						X			
Weight	X		X	X	X	X	X	X		
Vital Signs ¹²	X	WEEKLY	WEEKLY	MONTHLY	X	X	X	X	X	
12-lead ECG	X									
Procedures	Screen	Treatment Phase					Post Induction Phase		Long Term Follow-up	Survival Follow-up
		Cycle 1-2 Idelalisib only (Days 1-56)	Cycle 3 & 4 Weekly Ofa + Idelalisib ¹⁵	Cycle 5-8 Monthly Ofa + Idelalisib	Restage Cycle 4 day 22	Cycle 2 day 22 (Restage end of cycle 2), Cycle 10 day 1 (Final Restage 2 months after end of ofa therapy) and off treatment prior to cycle 10	Cycle 9 Day 1	Every 2 mos while on study drug beginning Cycle 10	Every 3 or 6 months ¹¹	Yearly

CONFIDENTIAL

This document is confidential. Do not disclose or use except as authorized.

Adverse Events	X	WEEKLY	WITH PE	WITH PE	X	X	X	X	X ⁸	
Concomitant Therapy	X	WEEKLY	WITH PE	WITH PE	X	X	X	X		
Chemistry ¹³	X	WEEKLY ¹³	WEEKLY THROUGH H C4 D 22 ¹³	MONTHLY	X	X	X	X	X	
Hematology ¹⁴	X	WEEKLY	WEEKLY THROUGH H C4 D 22	MONTHLY	X	X	X	X	X	
Beta-2-microglobulin	X				X	X		EVERY 6 MOS	EVERY 6 MOS	
Immunoglobulins (IgG, IgM, IgA)	X				X	X		EVERY 6 MOS	EVERY 6 MOS	
Serum protein electrophoresis	X				X	X		EVERY 6 MOS	EVERY 6 MOS	
CD4 count	X				X	X		EVERY 6 MOS	EVERY 6 MOS	
Direct Coombs test	X									
Serum Pregnancy Test ⁹	X		MONTHLY	X		X		ONCE 5 MONTHS POST OFA		
Hepatitis B surface antigen and antibody ¹⁰ , Hepatitis C antibody, HIV	X									
Survival follow-up by telephone or clinic visit note										X

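### The post-treatment contraception periods in the eligibility criteria and in Section 5.3.4 contradict each other for both sexes, and the male clause in 5.3.4 can lapse at the last ofatumumab infusion

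*Combined protocol and SAP*

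**What the plan says.** All references are to the combined protocol and SAP.

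**Women**
- Section 3.1 (the second item numbered 3.1.1): contraception "from the screening visit throughout the study and for 30 days from the last dose of idelalisib". The sentence before it, which covers women and men, asks for contraception for as long as they take part in the study.
- Section 3.2.16 excludes women "unable or unwilling to use adequate contraception from study start to 30 days after the last dose of protocol therapy".
- Section 5.3.4 requires contraception during treatment and then for 30 days after study drug or "12 months from the last dose of ofatumumab (whichever is later").

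**Men**
- Section 3.2.17 excludes "Male subjects unable or unwilling to use adequate contraception methods from study start to 30 days after the last dose of protocol therapy".
- Section 5.3.4 requires contraception during the treatment period and "for 90 days following discontinuation of idelalisib". It names no period counted from ofatumumab.

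**Treatment status under the current amendment**
- Sections 2.5 and 5 say that idelalisib had been stopped in all patients by 11 March 2016.
- Section 5 lets patients already on ofatumumab complete the course, and lets those not yet at day 57 start it.
- Section 3 says that enrolment is closed. Section 14.1 gives the final number as 27.

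**The concern.** This is a safety instruction. Section 3.2.15 cites possible teratogenic or abortifacient effects of both agents, Section 3.1 says their effects on the fetus are unknown, and Section 11.1.2 requires reporting of pregnancies in participants and in the partners of male participants. An instruction with that purpose should have one end date.

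The March 2016 amendment made the inconsistency matter more. It separated the last idelalisib dose from the last ofatumumab dose, sometimes by months, but left the contraception clocks as they were. Section 3.1 (women) and Section 5.3.4 (men) still count from a drug that nobody is taking, while the drug still being given has a post-treatment window in 5.3.4 for women only.

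**Working it through.** The plan gives no figure to reproduce. The check sets the windows side by side and puts dates on them.

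**Inputs**
- S, the idelalisib stop: 11 March 2016 (Sections 2.5 and 5), taken here as the stop date for the illustration.
- Ofatumumab schedule (Sections 5 and 5.2.2): first dose on day 57, weekly to day 106, then day 1 of cycles 5 to 8; cycle 4 lasts 49 days, the others 28.
- Cycle 4 starts on day 57 + 28 = 85. Cycle 5 starts on day 85 + 49 = 134. Cycle 8 starts on day 134 + 3 × 28 = 218. The first-to-last span is 218 − 57 = 161 days. This agrees with weeks 20 and 32 in Section 5: 19 × 7 + 1 = 134 and 31 × 7 + 1 = 218.

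**Formulas.** Let L be the last ofatumumab infusion and d = L − S, with d at least 0.
- 3.2.16 and 3.2.17 end at L + 30 days.
- 5.3.4, women, ends at L + 12 months, the later of its two clocks when ofatumumab is the last drug given.
- 5.3.4, men, ends at the later of L and S + 90 days, taking the treatment period to end at the last infusion.
- 3.1, women, idelalisib clock alone: S + 30 days = 10 April 2016.

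**Results**, assuming no dosing delays, by which infusion fell on 11 March 2016:

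| Infusion on 11 Mar 2016 | d (days) | L | 3.2.16 / 3.2.17 | 5.3.4 women | 5.3.4 men | Men: 5.3.4 minus 3.2.17 |
|---|---|---|---|---|---|---|
| 1st (day 57) | 161 | 19 Aug 2016 | 18 Sep 2016 | 19 Aug 2017 | 19 Aug 2016 | −30 days |
| 5th (day 85) | 133 | 22 Jul 2016 | 21 Aug 2016 | 22 Jul 2017 | 22 Jul 2016 | −30 days |
| 9th (day 134) | 84 | 3 Jun 2016 | 3 Jul 2016 | 3 Jun 2017 | 9 Jun 2016 | −24 days |
| 12th (day 218) | 0 | 11 Mar 2016 | 10 Apr 2016 | 11 Mar 2017 | 9 Jun 2016 | +60 days |

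**Women.** In every row the gap between 3.2.16 and 5.3.4 is 365 − 30 = 335 days, about 11 months. Both are counted from the same infusion, so this is a direct conflict. It shrinks for a woman who had finished ofatumumab earlier and stayed on idelalisib until March 2016, because her last protocol therapy is then later than L.

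**Section 3.1.** The idelalisib clock alone ends on 10 April 2016, before the last infusion in the first three rows. The same sentence also requires contraception throughout the study, and Section 5.5 allows follow-up for up to 10 years. Depending on what counts as the study, this clock could be the shortest or the longest of the three.

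**Men.** The difference is 60 − d days for d up to 90, and −30 days beyond that. The two rules agree only at d = 60. Below that 5.3.4 is longer; above it 3.2.17 is longer. Once d exceeds 90, the idelalisib clock has run out before the last infusion and the male clause in 5.3.4 asks for nothing afterwards.

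**The case against.** The strongest reply is that the 30-day figures are eligibility criteria, applied at screening in a study now closed to enrolment, whereas Section 5.3.4 is the on-study instruction. A woman who follows 5.3.4 also satisfies 3.2.16, so the two can be obeyed together, and 5.3.4 names a medical monitor for questions. This has some force: a site could reasonably treat 5.3.4 as governing. But no passage says that it prevails. The criteria describe conduct after the last dose rather than a state on the day of screening, and post-ofatumumab periods could still be running under the amendment. Giving 5.3.4 priority would also leave its male clause, which can lapse at the last infusion.

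A reader might infer several stronger things that the documents do not support:
- **That the male windows differ by 60 days.** The 30 and 90 days start from different events. The end dates are 60 days apart only when no ofatumumab followed the idelalisib stop.
- **That anyone following the entry criteria would stop far earlier than 5.3.4 requires.** For men with more than 60 days of ofatumumab remaining, the entry criterion is the longer rule.
- **That the male window depends on idelalisib alone.** Section 5.3.4 also covers the treatment period, 3.2.17 counts from protocol therapy, and Section 3.1 asks men as well for contraception while they take part.
- **That the calendar's pregnancy test, "ONCE 5 MONTHS POST OFA", contradicts a 12-month window.** It is a testing time, and nothing requires testing for the whole contraception period.
- **That participants agreed to, or were told, a particular period.** The consent pages are not available and the contraception handout at the end is incomplete.

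**Conclusion.** The contradiction stands for both sexes. For women whose last protocol drug is ofatumumab, 3.2.16 and 5.3.4 end about 11 months apart, and Section 3.1 adds a clock with no clear end. For men the two rules start from different events: 5.3.4 runs from 60 days longer to 30 days shorter than 3.2.17, and beyond 90 days of remaining ofatumumab it has no post-infusion period at all.

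The dates assume an idelalisib stop on 11 March 2016, no dosing delays, and a treatment period that ends at the last infusion. An earlier idelalisib stop makes d larger and moves men further towards the −30-day end.

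The number affected is not stated. Section 14.1 gives 27 enrolled, Section 3.3 says that most women with CLL are postmenopausal, and Section 5 permits continued ofatumumab without saying how many patients took it up. The number of affected women could be zero. This limits the scale of the problem, not its correctness. It is an inconsistency in a safety instruction that should be corrected; it does not touch the endpoint, the sample size or the analysis. No view is taken on which period is right.

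**What to change.** Reconcile Sections 3.1, 3.2.16, 3.2.17 and 5.3.4 to one stated window per sex, each counted from a named last dose that takes account of ofatumumab continuing after idelalisib. State what is meant by the study, the treatment period and study drug in these clauses, so that the end date can be computed for each participant. The choice of period belongs to the sponsor-investigator and those responsible for safety.

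Then check the consent form and the contraception handout against the reconciled text, and inform any affected participants still on, or recently off, ofatumumab. The cost is an amendment to the wording, a check of participant materials and, where needed, a short notice. No data collection or analysis changes.
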